18.3.4. Monitoring PSA Progression

PSA levels will be measured and monitored by the investigator locally to make decisions during the OL study period. For details, refer to Schedule of Activities (Table 16).

Time to PSA progression is defined in Section 10.4.2.1.

For patients who have been in treatment suspension since Week 37 for undetectable (<0.2 ng/ml) PSA values at Week 36, the study investigator will directly monitor and assess the patient's locally obtained PSA levels. Open-labeled treatment will be reinitiated if subsequent local laboratory PSA values increase to ≥ 2.0 ng/mL for patients with prior prostatectomy, or ≥ 5.0 ng/mL for patients who had prior radiation therapy. If laboratory PSA values meet the requirement for treatment reinitiation, the patient should return to the study site as soon as possible for drug dispensing and reinitiation of study treatment.

Treatment reinitiation must be registered in the IWRS to obtain the enzalutamide treatment for patients on the enzalutamide treatment arms and provision of a 12 week supply of study drug for resumption of treatment. (Refer to the IWRS Site Manual). If a patient is on the leuprolide arm, they will restart leuprolide and continue with their subsequent IP administration (including leuprolide as applicable) at their next study visit. Study drug administration should continue regardless of PSA values until radiographic progression is confirmed by local imaging (CT/MRI) per investigator's assessment and the investigator considers continuing study drug not to be beneficial.

A prostate cancer nomogram will be provided to investigational sites for uniform calculation of the PSA doubling time.^[25]

18.4. Investigational Product

18.4.1. Enzalutamide Administration, Storage, and Accountability

All patients will self-administer four 40-mg soft gelatin enzalutamide capsules (160 mg/day) by mouth once daily with or without food, unless they were receiving a reduced dose during double-blind treatment (open-labeled treatment will continue at the reduced dose). Patients should return all study drug bottles, including unused study drug to the site as indicated in the study drug accountability visits (Table 16).

Enzalutamide should be handled and stored safely and properly in accordance with the study drug label. Study site personnel must make all reasonable efforts to obtain all bottles and unused study drug from patients who do not routinely return the bottles at study site visits.

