18.1. Rationale and Treatment Plan

Primary endpoint analyses demonstrated that the primary efficacy endpoint of metastasis free survival (MFS) was established and the safety profile of enzalutamide was confirmed, therefore, the treatment codes for all patients will be unblinded and an open-label treatment period is being implemented. The final analysis of the key secondary endpoint for overall survival (OS) will be performed as planned. Patients will continue to receive their originally assigned study treatment in this open-label (OL) study period. Patients assigned to the placebo plus leuprolide arm will no longer take the placebo capsules. No crossover treatment will be implemented.

For patients whose cancer has not progressed radiographically, locally (change was effective as of 31-Mar-2023) performed scans (CT/MRI and bone scan) will be conducted until the patient's cancer progresses radiographically. Scans read centrally by blinded independent central reviewer (BICR) ceased as of 31-Mar-2023. Prostate-specific antigen (PSA) levels will also be done at a local lab and monitored by the investigator per standard of care (SOC) effective date of 31-May-2023. Patients who are in treatment suspension (due to prior undetectable PSA at study Week 36) will continue to have their PSA values, done at the local lab, evaluated by the investigator every 3 months for possible treatment reinitiation per protocol criteria. For details, refer to [Table 16](#).

Patients who discontinue study treatment or withdraw consent for further treatment will continue safety follow-up and long-term follow-up assessments per protocol (see [Section 18.8](#)). Long-term follow-up data including survival status, documentation of new antineoplastic therapies for prostate cancer, skeletal-related events, and progression on first subsequent therapy (PFS2) will be collected every 12 weeks until the final OS analysis. The associated endpoints will be summarized descriptively at the time of the final OS analysis.

Patients who receive any treatment other than their assigned study treatment for prostate cancer after unblinding will not be eligible for this OL period. All patients who permanently discontinue study drug treatment will remain in the study, complete safety follow-up, and subsequently commence long-term follow-up.

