- Symptom directed and includes investigating any new abnormalities and assessment of vital signs per Institution's SOC.
- Per Institution's SOC, refer to Section 18.3.3 for radiographic assessments (CT Scan/MRI/Bone scan).
- For patients who permanently discontinue randomized study drug treatment before radiographic progression is identified and confirmed by local radiology review per protocol, continue radiographic assessments every 24 weeks (± 14 days) until radiographic progression is identified and confirmed by local radiology review per protocol. Refer to Section 18.3.3.
- Record use of radiation therapy (external beam radiation therapy or radionuclides) or surgery to bone for prostate cancer, findings of clinically apparent pathologic bone fracture or of spinal cord compression, and use of opiate and/or systemic antineoplastic therapy due to bone pain. Refer to Section 9.1.3.6.
- Collect serious and nonserious adverse event information from the time of signing of informed consent through safety follow-up. If no safety follow-up, collect adverse event information through 30 days after the last dose of study drug. Contact patients for survival follow-up if they do not come to the clinic per Section 8.
- Only new concomitant medications for prostate cancer, hormonal, antineoplastic therapies and opiates

Table 16. Supplement Table 1: Study Schedule of Activities (Open-Label Period)

Study Period or Visit Abbreviations used in this table may be found in Appendix 7	Treatment			Un-scheduled	Safety FU	Long-Term FU
	1	Wk 13 & Every 12 wks	Wk 25 & Every 6 months			
Study Week	1	Wk 13 & Every 12 wks	Wk 25 & Every 6 months	Varies [2]	Varies [3]	Every 12 wks
Study Day	1 [1]	85	169	na	na	Every 84 days
Windows [4]	na	±5	±7	na	±7	±7

should be reported per Section [18.6](#).

12. Contraceptive review per Section [8.2.3](#) applicable through 3 months after the last dose of study drug or per local guidelines.
13. Specific study drug treatment (ie, enzalutamide, enzalutamide plus leuprolide, or leuprolide) is based on randomized treatment assignment.
14. For patients resuming study drug after treatment suspension, if applicable.
15. Leuprolide acetate (leuprorelin acetate), 22.5 mg will be given as a single intramuscular or subcutaneous injection once every 12 weeks.

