18.4.2. Leuprolide Administration, Storage, and Accountability

For patients receiving leuprolide acetate (leuprorelin acetate), 22.5 mg will be given as a single intramuscular or subcutaneous injection once every 12 weeks.

The leuprolide acetate formulation for intramuscular injection is supplied as sterile lyophilized microspheres along with an accompanying diluent. The microspheres are to be reconstituted as described in the prescribing information and administered as a single intramuscular injection of 22.5 mg once every 12 weeks.

The leuprolide acetate formulation for subcutaneous injection is supplied as sterile powder along with an accompanying liquid gel solution. The powder is to be mixed with the liquid as described in the prescribing information and administered in clinic by study site personnel as a single subcutaneous injection of 22.5 mg once every 12 weeks.

Leuprolide should be handled and stored safely and properly in accordance with the prescribing information. Pfizer does not permit the shipment of leuprolide by mail.

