18.9. Statistical Methods

The final analysis of overall survival is planned after approximately 271 deaths occur across the 3 arms. Analyses will be performed using a stratified log-rank test to compare OS for enzalutamide plus leuprolide versus placebo plus leuprolide and for enzalutamide monotherapy versus placebo plus leuprolide on ITT population respectively.

The final analysis of the key secondary endpoint OS will be performed as planned (Section 10.4.2). Based on the planned testing procedure in Section 10.4.2 and the actual results from tests for the primary endpoint and key secondary endpoint at the time of final analysis for primary endpoint, the analysis of OS for the combination arm will be tested at the alpha level of 0.05. The analysis of OS for the monotherapy comparison will be tested hierarchically as planned at the same alpha level as the combination arm comparison if significant (Figure 2 and Table 15).

In the final OS analysis, the significance level will be adjusted for the interim OS analysis following the specified Haybittle-Peto efficacy boundaries (Section 10.8 and Table 15).

The analysis of OS in the aforementioned final analyses will be based on an ITT approach, and will be performed as the SAP. An additional confounding factor for the OS analysis may come from patients who choose to access commercial enzalutamide, combination of enzalutamide and leuprolide and other commercially available treatments for the patients. The sponsors may explore the effect of crossover and post-study systemic anticancer therapy using rank-preserving structural failure time model (RPSFTM), and the inverse probability of censoring weighting (IPCW) method if appropriate. Justifications, limitations and assumptions of RPFSTM and IPCW methods will be provided with further details in SAP.

At the time of final analysis of OS, updated results from following secondary endpoints including time to first use of new antineoplastic therapy, time to first symptomatic skeletal event and progression free survival on first subsequent therapy will be summarized descriptively and provided as exploratory analysis. No other efficacy endpoints will be formally tested.

All exploratory efficacy analyses will be performed in ITT population.

Safety analyses will include all patients who receive 1 dose or partial dose of study drug (safety population). Safety data for the patients treated in OL stage will be summarized by double blinded stage and OL stage separately.

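### Section 18.4.1 gives the open-label enzalutamide instruction to all patients, which contradicts the protocol's own rule that controls do not cross over

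*Protocol*

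**What the plan says.** Protocol Section 18.4.1, the capsule instruction of the open-label supplement, reads: "All patients will self-administer four 40-mg soft gelatin enzalutamide capsules (160 mg/day) by mouth once daily". One exception follows: "unless they were receiving a reduced dose during double-blind treatment (open-labeled treatment will continue at the reduced dose". Nothing in the sentence limits it to particular randomized arms.

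Other parts of the same protocol say something different:

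- **Section 18.1** says of the control arm: "Patients assigned to the placebo plus leuprolide arm will no longer take the placebo capsules". It then adds: "No crossover treatment will be implemented". The open-label part of the synopsis says the same on both points.
- **Table 16, note 13**, attached to the row for enzalutamide dispensing through the IWRS: "Specific study drug treatment (ie, enzalutamide, enzalutamide plus leuprolide, or leuprolide) is based on randomized treatment assignment". Leuprolide alone is one of the three options listed.
- **Section 18.2** has patients continue on the treatment they were assigned.
- **Section 18.3.4**, on restarting after suspension: "Treatment reinitiation must be registered in the IWRS to obtain the enzalutamide treatment for patients on the enzalutamide treatment arms". Men on the leuprolide arm restart leuprolide.

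Section 18.4.2, the parallel section for the other drug, opens with a qualifier that 18.4.1 lacks: "For patients receiving leuprolide acetate (leuprorelin acetate), 22.5 mg will be given as a single intramuscular or subcutaneous injection".

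On the analysis still to come, Section 18.9 states: "The final analysis of overall survival is planned after approximately 271 deaths occur across the 3 arms". That section and SAP Section 5.1.2 make OS the only efficacy endpoint to be formally tested at that point, on an intent-to-treat (ITT) basis.

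**The concern.** An instruction on who takes the capsules should agree with the rule on who is assigned them. Read on its own, Section 18.4.1 includes the placebo plus leuprolide arm. Read with Section 18.1, that arm takes no capsules at all.

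Two things would be at stake if a site acted on the literal wording. Men randomized to leuprolide alone would receive a study drug they were not assigned. The OS comparison would also lose part of its treatment contrast. The open-label period starts after the final MFS analysis, which is also the OS interim, so a large part of the OS information is still to accrue. The monotherapy OS comparison uses the same controls and would be diluted in the same way.

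**Working it through.** **1. The passages side by side**

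| Place | Who receives enzalutamide in the open-label period |
|---|---|
| 18.4.1 | All patients; exception for a previously reduced dose only |
| Synopsis, open-label period | By original assignment; placebo capsules stop; no crossover |
| 18.1 | Same as synopsis |
| 18.2 | By assignment |
| Table 16 note 13 | By randomized arm, with leuprolide alone as an option |
| 18.3.4 | Enzalutamide arms, at restart after suspension |

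The exception in 18.4.1 concerns how many capsules are taken. It does not take the control arm out of the sentence, so the contradiction remains on a plain reading.

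**2. The plan's own OS power**

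Inputs (Protocol 10.7 and Table 15; SAP 5.1.1 and Table 3): 191 deaths in the two blinded arms, hazard ratio (HR) 0.67, two-sided alpha 0.05, 1:1 allocation within the pair.

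Schoenfeld: power = Φ(√d / 2 × |ln HR| − z).

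√191 / 2 = 6.910; |ln 0.67| = 0.4005; product 2.767; minus 1.960 = 0.807; Φ(0.807) = 79.0%.

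The plan states 79.0%. At alpha 0.03 and 0.02 the formula gives 72.5% and 67.0%, against the stated 72.3% and 67.0%. The planned figures reproduce.

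**3. How much OS information is still to come**

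Table 15 expects 82 blinded-arm deaths at the interim. That leaves 191 − 82 = 109, or 109/191 = 57%.

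**4. Illustrative dilution**

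Let f be the share of control-arm risk switched to enzalutamide after the interim. The documents give no value for f, so it is an assumption and is shown across its whole range. Assume also that a switched control gets the full benefit at once.

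- HR after the interim: HR₂ = 0.67 / ((1 − f) + 0.67f)
- Overall HR: exp[(82 × ln 0.67 + 109 × ln HR₂) / 191]
- Power: the formula in step 2, with the overall HR

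For f = 0.25: HR₂ = 0.67 / 0.9175 = 0.730. Overall ln HR = (82 × (−0.4005) + 109 × (−0.3144)) / 191 = −0.351, so HR = 0.704. Power = Φ(6.910 × 0.351 − 1.960) = Φ(0.468) = 68.0%.

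| f (assumed) | HR after interim | Overall HR | Power |
|---|---|---|---|
| 0 | 0.670 | 0.670 | 79.0% |
| 0.10 | 0.693 | 0.683 | 75.0% |
| 0.25 | 0.730 | 0.704 | 68.0% |
| 0.50 | 0.802 | 0.743 | 53.8% |
| 0.75 | 0.890 | 0.788 | 37.7% |
| 1.00 | 1.000 | 0.842 | 22.0% |

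The calculation treats all 109 later deaths as exposed. Some can fall between the interim cut-off and a site's open-label Day 1, which Section 18.2 allows up to 16 weeks after ethics approval. Others can occur among men never eligible for open-label treatment: those with radiographic progression, or those who took other prostate cancer therapy after unblinding.

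**The case against.** The strongest reply is that this is one loose word. The sentence sits under a heading about enzalutamide and describes how the drug is taken. It is not where treatment is assigned, and every passage that does assign treatment agrees. Capsules are dispensed through the IWRS, and Table 16 ties that row to the randomized arm, so a control could take enzalutamide from the study only if the system supplied it against his allocation. This stands, and it makes actual crossover by this route unlikely. It does not remove the contradiction: the next section shows how the protocol writes a limit on patients, and 18.4.1 has none.

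Some stronger readings are tempting but not supported:

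- **That controls were crossed over, or that the OS result is compromised.** Nothing in the documents shows that a control received study enzalutamide.
- **That sites are left with no workable instruction.** The assignment passages and the IWRS give them one.
- **That 18.4.1 puts suspended men back on capsules, or moves a placebo patient on fewer capsules to a reduced enzalutamide dose.** Sections 18.1 and 18.3.4 govern suspension and restart separately, and 18.1 ends placebo capsules, so both readings are over-literal.
- **That a collapse in power is the expected result.** Starting from a later HR of 0.85, 0.90 or 1.0 gives 45%, 36% or 22%. But 0.85 already implies f of about 0.64, since 0.67/0.85 = 0.788 = 1 − 0.33f. The milder cases belong in the picture.

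The OS test is also ITT, so dilution would cost power rather than inflate type I error. Protocol 18.9 and SAP 6.2.4 already foresee commercial access to enzalutamide, with optional RPSFTM and IPCW analyses. A perfectly preserved contrast was therefore never assumed, although those analyses do not correct an instruction to sites.

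**Conclusion.** The contradiction is real. Section 18.4.1 covers all patients with an exception for dose level only. The synopsis, Section 18.1, Table 16 note 13 and Section 18.3.4 keep enzalutamide to the arms randomized to it. It is most likely a drafting slip with a low chance of harm.

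The case for correcting it rests on the consequence if it were followed and on the small cost of the change, not on likelihood. The size is conditional: from 79.0% power to about 75% if a tenth of later control-arm risk were switched, and to 22% if all of it were. These figures assume HR 0.67 up to the interim, immediate full benefit after switching, and exposure of all 109 later deaths. They illustrate sensitivity and are not a forecast.

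**What to change.** Reconcile Section 18.4.1 with the synopsis, Section 18.1, Table 16 note 13 and Section 18.3.4. One consistent statement should say which randomized arms, and which treatment states (active or suspended), the capsule instruction covers. The choice of wording is for the sponsor; no dose or clinical rule is proposed here. Communicate the result to sites by administrative letter or in the next amendment.

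As an option, check existing IWRS dispensing records to confirm that no enzalutamide was supplied off assignment.

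The cost is one sentence and a letter, plus the record check if it is done. The OS design, event target and alpha do not change.

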18.4.2. Leuprolide Administration, Storage, and Accountability

For patients receiving leuprolide acetate (leuprorelin acetate), 22.5 mg will be given as a single intramuscular or subcutaneous injection once every 12 weeks.

The leuprolide acetate formulation for intramuscular injection is supplied as sterile lyophilized microspheres along with an accompanying diluent. The microspheres are to be reconstituted as described in the prescribing information and administered as a single intramuscular injection of 22.5 mg once every 12 weeks.

The leuprolide acetate formulation for subcutaneous injection is supplied as sterile powder along with an accompanying liquid gel solution. The powder is to be mixed with the liquid as described in the prescribing information and administered in clinic by study site personnel as a single subcutaneous injection of 22.5 mg once every 12 weeks.

Leuprolide should be handled and stored safely and properly in accordance with the prescribing information. Pfizer does not permit the shipment of leuprolide by mail.

18.4.3. Shipment of Enzalutamide to Study Participants

Enzalutamide may be shipped by courier to study participants if permitted by local regulations and in accordance with storage and transportation requirements for enzalutamide. The tracking record of shipments, including temperature monitoring data, and the chain of custody of enzalutamide must be kept in the participant's source documents/medical records.

18.5. Duration of Treatment and Dose Modification

Open-label study treatment administration may continue for patients whose prostate cancer has not progressed radiographically.

Enzalutamide dose modification: patients who experience a grade 3 or higher toxicity that cannot be ameliorated by the use of adequate medical intervention may interrupt treatment for 1 week or until the toxicity grade improves to grade 2 or lower severity. Subsequently, study drug dosing may be restarted at the original dose (4 capsules/day [160 mg/day]) or a reduced dose (3 or 2 capsules/day [120 or 80 mg/day]) in consultation with the medical monitor.

There are no provisions for dose modification of leuprolide on this study. If enzalutamide is coadministered with a strong CYP2C8 inhibitor (eg, gemfibrozil), the dose of enzalutamide should be reduced to 80 mg once daily. If coadministration of the strong CYP2C8 inhibitor is discontinued, the enzalutamide dose should return to the dose used prior to initiation of the strong CYP2C8 inhibitor.

18.6. Concomitant Medications – Follow-up Anticancer Medications

Concomitant medications will be assessed at all clinic visits. Record only concomitant medications given for prostate cancer, hormonal therapies, antineoplastic therapies, and opioids on the concomitant medication CRF. All other concomitant medications do not need to be added to the concomitant medication CRF in this OL study period. Additionally, the use of any medication given during the study that is due to an adverse event is no longer required to be entered in the concomitant medication CRF but, the adverse event for which the drug was prescribed should be recorded on the adverse event CRF and in the patient's clinical record.

The use of concurrent cytotoxic chemotherapy or investigational anticancer agents while on study treatment is prohibited. Initiation of bisphosphonates or denosumab for bone health is now allowed and SOC supplementation with calcium and vitamin D is encouraged.

18.7. Treatment Interruption and Discontinuation

Patients whose treatment is interrupted due to an adverse event and restarted will continue to have regularly scheduled study visits based on their enrollment date in the OL period.

Permanent treatment discontinuation is defined as cessation of randomized study drug treatment administration. *Temporary* treatment interruption (eg, due to an adverse event) is not considered permanent discontinuation. For more details, refer to [Section 5.3](#). Safety follow-up will be performed per [Table 17](#). Information on study discontinuation related to COVID-19 is provided in [Appendix 6](#).

Sponsor discontinuation of study: The sponsor has the right to terminate the study anytime. However, the sponsor will ensure that study treatment will be available to all patients who participate in the OL period for as long as they are deriving clinical benefit.

Patients who discontinue study treatment (with exception of patients who withdraw consent) will have safety follow-up approximately 30 days after the last dose or before initiating treatment with a cytotoxic chemotherapy or investigational agent for prostate cancer. If a new cytotoxic or investigational anti-cancer treatment is initiated before 30 days after the last dose of enzalutamide/leuprolide, then safety follow-up should occur immediately before starting the new treatment. Long-term follow-up will commence after completion of safety follow-up. For more details, refer to [Section 18.8](#).

